5.5.2.2. Incomplete Stop Date

The following rules will be applied to impute the missing numerical fields. If the date of the last dose of double-blind study drug is missing, replace it with the last visit date or data cut-off date if the subject is on-going. If the imputed stop date is before the start date (imputed or non-imputed start date), then the imputed stop date will be equal to the start date.

Missing day and month

- If the year of the incomplete stop date is the same as the year of the date of the last dose of double-blind study drug, then the day and month of the date of the last dose of double-blind study drug will be assigned to the missing fields.
- If the year of the incomplete stop date is prior to the year of the date of the last dose of double-blind study drug, then December 31 will be assigned to the missing fields.
- If the year of the incomplete stop date is after the year of the date of the last dose of double-blind study drug, then January 1 will be assigned to the missing fields.

Missing month only

• The day will be treated as missing and both month and day will be replaced according to the above procedure.

Missing day only

• If the month and year of the incomplete stop date are the same as the month and year of the date of the last dose of double-blind study drug, then the day of the date of the last dose of double-blind study drug will be assigned to the missing day.

• If either the year is before the year of the date of the last dose of double-blind study drug or if both years are the same but the month is before the month of the date of the last dose of double-blind study drug, then the last day of the month will be assigned to the missing day.

• If either the year is after the year of the date of the last dose of double-blind study drug or if both years are the same but the month is after the month of the date of the last dose of double-blind study drug, then the first day of the month will be assigned to the missing day.

5.6. Pulmonary Exacerbation Definitions

A respiratory event evaluation form has been developed to collect CF pulmonary exacerbation information from the physician perspective. This form is designed to systematically characterize health-care provider observations related to exacerbations, and to allow categorization and scoring consistent with Fuch's or Rosenfeld CF exacerbation definitions. The data generated from these forms will provide the basis for recording incidence and rate of pulmonary exacerbations.

The following 12 Fuchs' signs and symptoms will be assessed in the definitions of Fuch's, modified Fuch's, and expanded Fuch's exacerbation.

- 1. Increased cough
- 2. Change in sputum volume, color, or consistency
- 3. New or increased hemoptysis
- 4. Increased dyspnea during moderate exertion, during mild exertion, or at rest
- 5. Sinus pain or tenderness
- 6. Change in sinus discharge
- 7. Malaise, fatigue, or lethargy
- 8. Anorexia or weight loss
- 9. Temperature above 38°C
- 10. Change in findings on chest examination
- 11. Relative 10% decrease in %-predicted FEV₁
- 12. Chest radiography results consistent with pulmonary infection

The modified Fuchs exacerbation is defined as the presence of at least 4 of 12 Fuchs' signs and symptoms without the requirement for treatment with antibiotics [Rowe 2012].

The expanded Fuchs exacerbation is defined as the presence of at least 4 of 12 Fuchs' signs and symptoms requiring treatment with any form of antibiotic treatment [inhaled, oral, or intravenous]. This antibiotic treatment is defined either as the addition of new antibiotics or an

increase in the dose of an existing antibiotics within 14 days of the pulmonary exacerbation start/stop date.

The classic Fuchs exacerbation is defined as the presence of at least 4 of 12 Fuchs' signs and symptoms requiring treatment with parenteral antibiotics. This antibiotic treatment is defined either as the addition of new antibiotics or an increase in the dose of an existing antibiotics within 14 days of the pulmonary exacerbation start/stop date.

Pulmonary exacerbation based on investigator's assessments is recorded in the conclusion of respiratory event evaluation form.

6. ANALYSIS CHANGES FROM PROTOCOL

Due to the premature termination of the study, the time of withdrawal from the study analysis and 48-week completer and whole study completer analyses have been removed compared to current protocol version 1.0. The paried t-test on FEV₁ and the summary analysis of FEF₂₅₋₇₅, CFQ-R domain scores, and ataluren plasma concentrations have also been removed. Additionally the summary of incidences, rates, and durations of interventions (eg, antibiotic use and hospitalization) and disruptions to daily living (eg, missed school or work) resulting from pulmonary symptoms has been removed. On the other hand, the drug exposure adjusted incidence rate of TEAEs has been added. Summary of occurrence of TEAE has been added as well.

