2.2.2. Secondary Objectives

The secondary objectives are:

- To evaluate the long-term effect of ataluren on pulmonary function
- To evaluate the long-term effect of ataluren on pulmonary exacerbation
- To determine the long-term effect of ataluren on medical interventions
- To evaluate the long-term effect of ataluren on HRQL
- To evaluate the long-term effect of ataluren on general well-being
- To assess long-term ataluren plasma exposure

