2.3.2. Secondary Endpoints

- Changes in FEV₁, FVC, and FEF₂₅₋₇₅ as assessed by spirometry
- Rate of pulmonary exacerbations (modified Fuchs criteria)

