4.12.5. Pharmacokinetics Analyses

Ataluren plasma concentrations will be listed. For ataluren plasma concentrations, those that are below the limit of quantification will be identified by "BQ" in listings. Those values that are missing will be left blank in listings.

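### SAP Section 6 drops the planned summaries of CFQ-R, plasma concentrations, interventions and FEF25-75 but keeps the objectives or endpoints they serve, so 3 of 6 secondary objectives lose their planned summary

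*SAP*

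**What the plan says.** SAP 2.2.2 carries over all six secondary objectives from the protocol. Three matter most here: "To evaluate the long-term effect of ataluren on HRQL", "To assess long-term ataluren plasma exposure", and the objective on medical interventions. SAP 2.3.2 keeps changes in FEV1, FVC and FEF25-75 "as assessed by spirometry" as a secondary endpoint, and SAP 2.3.3 keeps pre-dose plasma concentration as a tertiary endpoint. CFQ-R and interventions no longer appear in the SAP endpoint lists.

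The protocol planned a descriptive summary for each:
- CFQ-R domains by visit, with the respiratory domain as the main one (11.4.7.3).
- Plasma concentrations by visit (11.4.7.2).
- Incidences, rates and durations of interventions and disruptions, with rates and durations adjusted for exposure (11.4.7.4).
- FEF25-75, analysed in the same way as FEV1 (11.4.6.1).

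SAP Section 6 states that FEF25-75, "CFQ-R domain scores, and ataluren plasma concentrations have also been removed" from the summary analyses. It then removes "the summary of incidences, rates, and durations of interventions" and of disruptions to daily living. Its opening sentence gives early termination as the reason for removing the withdrawal-time and completer analyses. The sentences that remove these four summaries give no separate reason. For concentrations, SAP 4.12.5 leaves this: "Ataluren plasma concentrations will be listed".

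**The concern.** The SAP states objectives and endpoints that its own analysis sections do not summarise. A reader of the study report would find quality of life, interventions and plasma exposure named as things the study set out to evaluate, with no planned table answering them. The blanket reason, early termination, fits analyses that need patients to reach a fixed time point. It fits poorly for tables that describe whatever was observed at each visit.

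At stake is whether a study with long-term exposure data can report on its own secondary objectives. The primary safety objective is not affected. No hypothesis test, alpha or power depends on the point, because SAP 4.2 describes all analyses as descriptive.

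**Working it through.** The plan gives no figure to reproduce here. The check is a count of objectives against analyses, then a comparison of visit schedules, then an estimate of how much follow-up termination left.

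**1. Objectives (SAP 2.2.2) against analyses (SAP 4.8 to 4.12) and removals (SAP 6)**

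| Secondary objective | What remains in the SAP | Planned summary kept? |
|---|---|---|
| Pulmonary function | FEV1 (4.11.1) and FVC (4.11.3) by visit; FEF25-75 removed | In part, 2 of 3 measures |
| Pulmonary exacerbation | Rates, counts and duration (4.11.2) | Yes |
| Medical interventions | Dedicated summary removed; indirect information only | No |
| HRQL | CFQ-R summary removed; by-subject CRF listings (4.1) | No |
| General well-being | Weight and BMI by visit (4.12.2), the measures Protocol 14.4.4 ties to well-being | Yes |
| Plasma exposure | Listing only (4.12.5) | No |

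Result: 2 kept, 1 kept in part, 3 without their planned summary.

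**2. Does termination separate the removed measures from those kept?**

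- FEF25-75 comes from the same spirometry as FEV1 and FVC, which are still summarised by visit, overall and by preceding Study 021 arm.
- The schedule (SAP Table 1) places CFQ-R at every visit from 1 to 9, the same visits as on-treatment spirometry.
- Protocol 7.1.2 calls for types and durations of intervention for exacerbations to be collected in the CRF. The respiratory event evaluation is scheduled at Visits 1 to 9.
- Plasma samples are scheduled at Weeks 24, 48, 72 and 96.
- The premature-discontinuation visit repeats the Week 96 procedures (Protocol 8.2.4). Patients stopped at termination were therefore due CFQ-R, spirometry, a respiratory event evaluation and a plasma sample.

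Nothing in the schedule makes a by-visit summary feasible for FEV1 and FVC but not for these measures.

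**3. How much follow-up did termination leave?**

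Inputs: first Study 021 dose on 15 August 2014, an estimated 14-month recruitment and 48 weeks of treatment (Protocol 1), and 2 March 2017 as the stop date (SAP 2.1). Assumptions, not given in the documents: uniform accrual, no gap at rollover, no dropout.

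- Earliest rollover: 15 August 2014 + 336 days = 17 July 2015. To 2 March 2017 is 594 days, and 594/7 = 84.9 weeks.
- Latest rollover: 15 October 2015 + 336 days = 15 September 2016. To 2 March 2017 is 168 days, and 168/7 = 24.0 weeks.
- Spread: 84.9 − 24.0 = 60.9 weeks.
- Share able to reach Week 48: (84.9 − 48)/60.9 = 36.9/60.9 = 61%.
- Week 72: (84.9 − 72)/60.9 = 12.9/60.9 = 21%.
- Week 84: (84.9 − 84)/60.9 = 0.9/60.9, about 1%. Week 96: none.

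The recruitment estimate may not have held. Expected Study 021 enrolment is about 208 in Protocol 11.1 and about 279 in SAP 2.4. If the enrolment rate stayed the same, the spread becomes 60.9 × 279/208 = 81.6 weeks. The Week 48 share is then 36.9/81.6 = 45% and the Week 72 share 12.9/81.6 = 16%. On these assumptions 45% to 61% could reach Week 48, before any dropout or rollover gap.

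**The case against.** Several points on the other side stand.

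- A reader might infer that the three objectives have no analysis at all. The documents do not support that. Concentrations are listed under a pharmacokinetics heading. For interventions, the expanded and classic Fuchs definitions (SAP 5.6) count exacerbations treated with antibiotics, and SAP 4.11.2 reports their rates. Concomitant medications and non-drug therapies are tabulated (SAP 4.8). Exacerbations needing admission are reportable as serious events (Protocol 9.1.2), and serious TEAEs are tabulated with occurrence counts (SAP 4.10.1). None of these gives intervention durations or missed school or work, so they address the objective only in part. CFQ-R is the clearest gap.
- Termination does bear on long-term summaries. By the estimate above, few patients reach Week 72 and none reach Week 96, so two of the four scheduled plasma times are sparse or empty apart from early-termination samples.
- The removals are disclosed in a dedicated section, and SAP Section 1 says that the SAP supersedes the protocol. Part of the defect is alignment, and relabelling the objectives would cure that part.
- A reader might also infer selective reporting, because the SAP is dated 14 July 2017, after termination of an open-label study. The documents do not show when the removals were decided, whether results had been reviewed, or when the database was locked. The timing is not evidence of selection.

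What does not stand is termination as a reason for removing all four summaries. Sparse late visits call for showing n. They do not call for dropping the earlier visits.

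**Conclusion.** The point holds as a mismatch between stated objectives and planned analyses. Three of six secondary objectives (HRQL, medical interventions, plasma exposure) lack their planned summary, and one of three spirometry measures is unanalysed although still named as an endpoint. The count rests only on the SAP text. Primary safety conclusions are untouched.

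The claim that useful data exist rests on the visit schedule and on the SAP's own retention of FEV1 and FVC by visit. It does not depend on the follow-up estimate. The 61% reaching Week 48 is an upper estimate under 14 months of uniform accrual, no rollover gap and no dropout, and it falls to 45% if recruitment lengthened in proportion to enrolment. The documents give no actual rollover or dropout figures.

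**What to change.** Amend the SAP, as its Section 1 allows before database lock, to restore the protocol's descriptive summaries with n shown at each visit:

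- CFQ-R domains by visit, respiratory domain first.
- FEF25-75 by visit, in the same form as FVC.
- Trough plasma concentrations by visit.
- Exposure-adjusted rates and durations of interventions and disruptions from pulmonary symptoms, with incidences.

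A split by preceding Study 021 arm is optional for CFQ-R and concentrations, since the protocol did not plan one. The completer analyses can stay removed.

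If the sponsor keeps any summary out, SAP 2.2.2 and 2.3 should mark that objective or endpoint as not assessed or listing only, and Section 6 should give a reason specific to it.

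The cost is a few extra tables on data already collected, with small n at late visits, plus the SAP wording. No test or multiplicity adjustment is needed.
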